14.4 Secondary efficacy analyses

The primary ANCOVA analysis based on the summary mean at 12 and 15 months will be repeated on the other quantitative efficacy endpoints (see above). The significance of the treatment effect on each quantitative endpoint will also be evaluated based on the difference compared to Placebo in change from baseline at each individual visit and in slope of progression over the duration of the study. The proportion of responders at 15 months will be assessed through a Generalized Linear Mixed Model (GLMM) featuring logistic regression, and admitting center as a random effect. Secondary analyses will be conducted at a two-sided 5% significance level.

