3. FLOW CHART

Visits	←Screening period→		←Treatment period→				
	V 0	V 1	V2/ 	V 3	V4/ 	V 5	V 6
Month		0	3-month	6-month	9-month	12-month	15-month
Day	-30 to -1	0	90 ± 8	180 ± 10	270 ± 10	360 ± 10	450 ± 10
Inclusion exclusion criteria	X	X					
Informed consent	X						
Demographic data & medical history	X						
Diagnosis history (DNA) & treatments	X						
Physical and neurological examination	X	X		X		X	X
Vital signs	X	X		X		X	X
Electrophysiology (nerve conduction studies)	X	X*		X		X	X
CMTNS-v2	X	X*		X		X	X
ONLS		X		X		X	X
9 Hole PEG		X		X		X	X
QMT (dorsiflexion & handgrip)		X		X		X	X
10 metres Walk Test		X		X		X	X
Euro QoL-5D		X		X		X	X
VAS / main impairment / disability		X		X		X	X
Review of concomitant treatments	X	X	X	X	X	X	X
Blood samples for safety	X	X*		X		X	X
Blood samples for PK		X		X		X	X
Blood samples for Biomarkers		X		X		X	X
ECG	X	X*					X
Skin Biopsy (optional ancillary sub-study)		X					X
Leg MRI (optional ancillary sub-study)		X					X
Treatment allocation		X					
Treatment dispensation		X	X	X	X	X	
Review of adverse events		X	X	X	X	X	X
Review of compliance			X	X	X	X	X

* Electrophysiological testing to assess CMTNS score, and blood sample and ECG for safety will not be re-assessed at randomization (Visit 1) if they were performed at screening (Visit 0) within the previous 14 days. If time between V0 and V1 is greater than 14 days they must be repeated at randomization to assess baseline.

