Considering that the ONLS is the best assessment method of disability, a clinically relevant endpoint in CMT1A, and it has been recently shown to be more sensitive to change than the CMTNS, the ONLS is selected as primary endpoint.

B. CMTNS is a specific scale designed to assess severity of impairment in CMT disease (Shy, 2005). Although not completely validated, it provides a single and reliable measure of CMT severity. It is a 36-point scale based on 9 items: 5 of them quantify impairment (sensory symptoms, pin sensibility, vibration, arm and leg strength), 2 activity limitations (motor symptoms arms and legs) and 2 electrophysiological data (amplitudes of ulnar Compound Muscle Action Potential [CMAP] and Sensory Nerve Action Potential [SNAP]). Increased scores indicate a worsening of the function: the scores categorize a disability as mild (0-10), moderate (11-20) and severe (21-36).

While CMTNS score is commonly used to assess disease severity, it may be problematic to evaluate the potential clinical benefit of a drug; as it is a composite score based on patient signs, symptoms, and on electrophysiological data with potentially very different meanings and interpretations, an objective analysis may be difficult.

Nevertheless, CMTNS is an accepted measure of CMT severity, but its sensitivity to change is debated (Reilly, Shy *et al.*, 2010). Some CMTNS components are apparently not sensitive enough, and floor/ceiling effects do occur. For instance, if the patient had surgery (fixation of the ankle), the 'motor leg symptoms' definitively score 3; so, it is not possible to get a decrease of the score whatever it happens. The usefulness of the SNAP component was also judged to be limited as it is frequently absent in CMT1A patients which receive the maximum score on their entry visit, thus has a low sensitivity to change. (Komyathy, Neal *et al.*, 2013) pointed out that sensory and motor symptoms items result from subjective opinion from patients, concerning their leg and arm strengths and loss of sensation in their legs, and that pin sensibility, vibration and strength are based on a neurological examination which depends on patient cooperation and examiner consistency to obtain reproducible results. Finally, some measurement of the CMTNS, such as SNAP or vibratory sensation, may decrease normally with age; thus, scores could increase slightly as age for reasons independent of CMT (Shy, 2005).

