- **Laboratory testing by the central laboratory**

Safety laboratory tests sampled at V0 and measured at the central laboratory are needed for checking the exclusion criteria. If any of the laboratory parameters are not available upon the end of the screening period (e.g., sample material damaged during transport etc.) a retest can be performed.

- **Assessment of inclusion/exclusion criteria**

The following information must be collected and documented in the CRF within the screening period:

- Patient history of **CMT1A with documented genetic diagnosis** should be noted in the source document;
 - If not already documented, blood sampling (4 ml) for the PMP22 duplication genetic test will be performed.
- Patient history of all the treatments including surgery, physiotherapy and medications must be notified in the source documentation prior randomization (with regimen, duration, and complications and their treatments);
- Demographics characteristics (age, gender, and ethnic origin);
- Physical examination including vital signs (SBP and DBP, heart rate), body height and weight;
- Physical and neurological examinations with the presence of weakness at dorsiflexion;
- Electrophysiological tests of sensory and motor responses of ulnar and radial nerves on the non-dominant side (including CMAP, SNAP, NCV, and DML parameters) will be performed to determine the CMTNS score;
- 12-lead ECG (sent for centralized reading by a cardiologist);
- Results of safety laboratory tests from the central laboratory;
- Authorized and prohibited concomitant medications.

11.2.2 Inclusion visit = Visit 1

At this Visit 1 the investigator must check that the patient meets all the inclusion criteria and none of the exclusion criteria.

The following assessments must be performed:

- physical and neurological examinations including vital signs (SBP and DBP, heart rate),
- clinical scores and functional tests at baseline:
 - CMTNS score to determine severity (electrophysiological testing performed during the screening period can be used. It should be repeated only if time between V0 and V1 is greater than 14 days)
 - ONLS score,
 - 9-Hole Peg Test in the non-dominant hand,
 - Quantified muscular testing (hand grip and foot dorsiflexion on both sides)
 - 10 m Walking test
- quality of life measured by:
 - EuroQol 5-Dimensional Health-related Quality of Life scale (EQ-5D);

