14.2 Primary efficacy analysis

The significance of the studied drug effect compared with Placebo will be tested by an Analysis of Covariance (ANCOVA) on the summary mean of ONLS at 12 and 15 months adjusted for baseline ONLS values. ANCOVA will be featured by a Linear Mixed Model (LMM), including baseline ONLS values and treatment as fixed factors, and center as random effect. The use of two repeated post-baseline measures increases the power to detect treatment differences in mean levels of the outcome measure over time (Frison and Pocock, 1992; Morgan and Case, 2013).

Two active doses will be compared to Placebo. As the monotonicity of dose effect is not assumed, each dose will be compared at a two-sided 2.5% significance level, in order to preserve an overall false-positive rate of 5%.

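### The CMTNS-v2 secondary ANCOVA adjusts for one baseline, although a screening score is also collected and could be added as a second covariate for a small precision gain

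*Combined protocol and SAP*

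**What the plan says.** - **Model.** Section 14.2 defines the primary model as an ANCOVA on the mean of the 12- and 15-month values, "including baseline ONLS values and treatment as fixed factors, and center as random effect". ONLS is measured before treatment only at V1, so one baseline is all that model can have.
- **Secondary endpoints.** Section 14.4: "The primary ANCOVA analysis based on the summary mean at 12 and 15 months will be repeated on the other quantitative efficacy endpoints". It has no rule for an endpoint that is also scored at V0, and secondary tests are at two-sided 5%.
- **Schedule.** The flow chart marks CMTNS-v2 at V0 (X) and V1 (X*). Its footnote reads "Electrophysiological testing to assess CMTNS score, and blood sample and ECG for safety will not be re-assessed at randomization (Visit 1") when they were done at V0 in the preceding 14 days. Otherwise: "If time between V0 and V1 is greater than 14 days they must be repeated at randomization to assess baseline".
- **V0 procedures (11.2.1).** Electrophysiological tests "will be performed to determine the CMTNS score". Inclusion criterion 3 needs a CMTNS-v2 above 2 and at most 18.
- **V1 procedures (11.2.2).** The assessments to be done include "CMTNS score to determine severity (electrophysiological testing performed during the screening period can be used").
- **Structure (8.4.1.3).** "It is a 36-point scale based on 9 items", of which two are electrophysiological (ulnar CMAP and SNAP amplitude).

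**The concern.** Section 14.2 justifies two post-baseline measures by the power that repeated measurement adds. The same summary-measure logic applies before treatment: a second baseline averages out short-term scoring noise and so predicts the outcome better. For CMTNS-v2 that second value exists because eligibility requires it, yet 14.4 carries over a model built for an endpoint with a single baseline.

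At stake is the width of the confidence interval for one clinical secondary endpoint. V0 precedes randomisation, so adjusting for it does not bias the treatment comparison.

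**Working it through.** **1. Which items are measured twice.** Of the nine items, each scored 0 to 4 (Appendix 3), two are electrophysiological: 8 of 36 points. The other seven (28 of 36 points) are clinical.
- Gap of 14 days or less: V1 may reuse the V0 electrophysiology, and 11.2.2 gives no such allowance for the clinical items.
- Gap over 14 days: all nine items are measured twice.

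The documents do not say what share of patients falls in each case.

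**2. Inputs.** None is given for CMTNS-v2. From section 14.3, for ONLS: R = 0.75, SD about 1, two post-baseline measures, compound symmetry, difference 0.3, two-sided 2.5%, 90% power. The V0-V1 correlation c is an assumption.

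**3. The plan's own figure.** With one baseline, the ANCOVA variance of the two-visit mean in SD² units is

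(1 + R)/2 − R² = 0.875 − 0.5625 = 0.3125.

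Per group, n = 2 × 0.3125 × (2.241 + 1.282)² / 0.3² = 86.2, so 87. The plan states 89, so this is close to the one-baseline, two-post-measure calculation behind it.

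**4. Adding V0.** If V0 and V1 each correlate R with the outcome and c with each other, the variance becomes

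(1 + R)/2 − 2R²/(1 + c) = 0.875 − 1.125/(1 + c).

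| Assumed c | Variance | Cut in variance | Cut in SE |
|---|---|---|---|
| 0.75 | 0.2321 | 25.7% | 13.8% |
| 0.85 | 0.2669 | 14.6% | 7.6% |
| 0.90 | 0.2829 | 9.5% | 4.9% |
| 0.95 | 0.2981 | 4.6% | 2.3% |
| 0.98 | 0.3068 | 1.8% | 0.9% |

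The first row treats two scores at most 30 days apart as no more alike than scores 12 to 15 months apart. It also needs a complete separate second score in every patient. It is the upper bound for R = 0.75 as long as c is not below R.

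**5. Partial second scores.** If only half the patients have a separate second score, a simple weighting halves the cut: 12.9% at c = 0.75, 4.7% at 0.90 and 2.3% at 0.95.

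**6. Sensitivity to R.** For c from 0.85 to 0.98, the cut runs from 5.7% to 0.7% if R = 0.6 (correlation between the two post-baseline visits kept at 0.75). It runs from 28.9% to 3.6% if R = 0.85 (that correlation also 0.85).

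**The case against.** **The second score may not be complete.** The asterisk sits on the CMTNS-v2 row itself. On a strict reading nothing in the score is redone within 14 days, and a second score is assured only for longer gaps. The V0 list in 11.2.1 also has no separate CMTNS-v2 scoring line. Against this, the footnote's subject is the electrophysiological testing, 11.2.2 lists the score among the V1 assessments, and both the flow chart and inclusion criterion 3 call for a V0 score. The better reading is that the seven clinical items are scored twice, but the ambiguity is real and supports the lower end of the range. Carried-over items also push the V0-V1 correlation up.

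**V1 is already the baseline.** The footnote ties the repeat beyond 14 days to assessing baseline, and one V1 covariate is a valid, conventional choice. This stands as a defence of validity. It does not bar V0 as an added covariate. Sections 14.5 and 14.9 also defer detail to an SAP, and no separate SAP text is in the documents.

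**The V0 score is used for selection.** Its range is truncated, which can weaken it as a covariate but does not bias a randomised comparison.

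**Stronger readings that a reader might infer.**
- That the plan gives up a quarter of the variance, enough to lift 80% power to 90% at two-sided 5%. That is the c = 0.75 row, with borrowed ONLS inputs.
- That both dose comparisons gain alike. The dose 2 arm was stopped early, and its missing values fall under the imputation in 14.5, so the gain applies mainly to dose 1 versus placebo.
- That CMAP, SNAP and NCV gain too. Where electrophysiology is not repeated, V0 and V1 are the same value and add nothing.
- That this answers the protocol's doubts about CMTNS sensitivity to change. Those doubts concern floor and ceiling effects and responsiveness, which a second baseline does not alter.

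**Conclusion.** The point holds as an optional efficiency gain. The plan implies one baseline covariate for CMTNS-v2 while a second pre-treatment score is scheduled and goes unused in the model. The size for CMTNS-v2 is unknown. Borrowing the ONLS inputs, a plausible cut in residual variance is about 2% to 15% (standard error about 1% to 8%), with 26% as the upper bound at R = 0.75, and less if some patients lack a separate second score. These figures assume compound symmetry apart from the V0-V1 correlation, equal correlation of V0 and V1 with the outcome, and complete 12- and 15-month data. The documents do not support calling the single-baseline analysis an error: it is valid, and nothing here touches bias, type I error, the primary ONLS analysis or the sample size.

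**What to change.** Add one sentence to 14.4. For the CMTNS-v2 total and its clinical sub-items, V1 is the named baseline, and the V0 score (or at least its seven clinical items) enters the 12/15-month ANCOVA as a second baseline covariate. Leave the ONLS model as it is, and do not extend the change to CMAP, SNAP and NCV. Change-from-baseline displays continue to use V1.

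Cost: the sentence and one degree of freedom per model, with no new data. Specify it before unblinding.

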V1.4	05DEC2017	Rationale for moving from V1.4 to V1.5: due to an unexpected investigational medicinal product (IMP) quality event, without safety concerns, the use of dose 2 IMP is discontinued from the pivotal phase III study CLN-PXT3003-02 upon Sponsor decision (September 18 th , 2017). The stability testing at Quay Pharma (UK) observed the occurrence of crystals in one stability batch of PXT3003 dose 2 at month 18 (September 14 th , 2017), whereas this was not the case at month 12. This new finding is inconsistent with the dose 2 IMP release criteria and therefore does not meet the ICH Harmonized Tripartite Guideline for Stability Testing of New Drug Substances and Products. Hence, the patient arm of PXT3003 dose 2 will early terminate the study. They will be offered to enter the extension study CLN-PXT3003-03 to receive the equivalent of dose 2 (5 mL per administration), by using of its equivalent dose, i.e. twice the dose 1 IMP (2x5 mL, i.e. 10 mL) per administration. Furthermore, all patients using dose 1 IMP or placebo will continue to receive dose 1 IMP or placebo (5 mL per administration) in the pivotal phase III study CLN-PXT3003-02 as planned.

IMPACTED OF THE PROTOCOL AMENDMENT V1.4

1. How to manage the dose 2 patient group discontinuation?	
The PXT3003 dose 2 study arm will discontinue prematurely from study CLN-PXT3003-02, in accordance with section 11.6.1 "if the study is prematurely discontinued then enrolled patients should be called for an end of study visit".
 
Hence, there is no need to implement additional information in the protocol.
 
The sites will receive additional useful instructions to organise the recall of dose 2 IMP patients.

2 Statistical sections: how to manage incomplete data	
Due to incomplete data in the dose 2 arm, the missing data will be evaluated as described in the section 14.5 of the protocol.

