8.4.1.2 Secondary efficacy endpoints

In the context of an orphan disease, when there are no ideal endpoints, it might be acceptable to assess multiple endpoints and to observe their outcomes. However, they have been selected according to our experience from the previous phase 2 study, and they are hierarchized as following:

- Responders Rate to PXT3003 therapy defined as a patients improving on ONLS at end of treatment.
- Clinical and functional tests:
 - Arm and leg sub-items of ONLS,
 - Charcot-Marie-Tooth Neuropathy Score version 2 (CMTNS-V2), total score and sub-items,
 - Nine-Hole Peg Test (9-HPT) performed on the non-dominant hand,
 - Hand grip Quantified Muscular Testing (QMT) and foot dorsiflexion QMT performed on both sides,
 - Time to walk 10 meters,
- Exploratory efficacy endpoints:
 - Electrophysiological parameters assessing sensory and motor responses of ulnar and radial nerves (non-dominant side):
 - Compound Muscle Action Potential (CMAP) on ulnar nerve,
 - Sensory Nerve Action Potential (SNAP) on radial nerve,
 - Nerve conduction velocity (NCV),
 - Quality of life measured by:
 - EuroQol 5-Dimensional Health-related Quality of Life scale (EQ-5D),
 - VAS on self-assessment of the individualized main impairment in daily activities defined at baseline with the patient,

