10.5 Dispensing and drug accountability

The study treatment will be dispensed only under restricted conditions as defined in the present protocol. Once the eligibility of the patient is confirmed by the investigator (all inclusion and exclusion criteria checked), **patients will be assigned a randomization number** according to the randomization process in the interactive web randomization system (**IWRS**) and dispensed a corresponding study drug kit.

The treatment will be dispensed only by the investigator under his/hers direct supervision or the pharmacist. Adequate records on receipt, dispensation, initials of the person dispensing the drug, use, return, loss, or other disposition of medication must be maintained. These records include dates, quantities, batch numbers, expiration dates, subject identification (initials) and the unique code numbers assigned to the study patients.

Patients will receive at each visit the necessary quantity of treatment until the subsequent one (including extra bottle(s) to cover for a potential delay [+/- one week] in study visits or any problem of study drug conservation). This will correspond to **3 boxes of 4 bottles of PXT3003 every 3 months**. The actual boxes to be dispensed will be **assigned by the IWRS**. Treatment should be taken until the last visit (at 15 months).

Study drugs must only be used for the study purpose and must not be used outside this protocol.

Patients should return empty and partially emptied or unused bottles to the hospital at each visit to receive (a) new kit(s).

At each visit the compliance/adherence to the treatment will be investigated: details of the quantities of bottles of medication dispensed and the count of used bottles returned will be recorded at each visit to report the compliance.

The patients will be asked whether the investigational treatment was taken as prescribed. If not, any change in the treatment and the number of forgotten intakes will be recorded. In addition, the number of quantities will be counted and compared to the theoretical quantities. Any mismatch will be investigated and justified in collaboration with the patient if possible.

Patients should be **instructed to store study medication in the refrigerator** (both unused and opened bottles). **However, transportation from the investigator's site to the patient's home can be done at ambient temperature (<30°C).**

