14. STATISTICAL CONSIDERATIONS

14.1 Analysis sets

The **Full Analysis Set (FAS)** will be constituted by all the randomized patients.

The **Per-Protocol (PP)** population will include all the patients of the FAS without major protocol violation during the course of the study.

All the efficacy analyses will be conducted on the FAS population and reproduced on the PP population for sensitivity purposes. The safety analyses will be conducted on the FAS, given that all randomized patients will receive at least one dose of treatment.

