14.5 Missing data

Few missing data were observed in past trials in this pathology. Due to likely expected loss of efficacy after treatment discontinuation, and a possible deterioration compared with baseline values, last or baseline observation carried forward may not be appropriate. Missing values will be imputed using a linear model estimated on the Placebo group. The potential impact of missing data on the study's conclusions will be evaluated. Descriptive data analyses will allow assessing the pattern of missing data, including reasons for drop-outs in each treatment group. In addition, sensitivity analyses will be conducted by using other missing data approaches (further details in the SAP).

For any patient experiencing early trial interruption, an early interruption visit is planned. It will be checked if this visit took place within a given time frame where the next regular visit would have been planned. In case the early interruption visit occurs within this time frame, data of the early interruption visit will be shifted to the next regular visit for all analyses. In case the early interruption visit does not occur within this time frame, the data of the early interruption visit will not be included in any of the inferential analyses.

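### Responder status at 15 months should not be read off a predicted ONLS mean: with dose 2 heavily imputed from the Placebo model, this biases the responder comparison even when the drug does nothing

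*Combined protocol and SAP*

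**What the plan says.** - Section 8.4.1.2 lists this secondary endpoint first: "Responders Rate to PXT3003 therapy defined as a patients improving on ONLS at end of treatment". It gives no size of change.
- Section 14.4 sets the analysis: "The proportion of responders at 15 months will be assessed through a Generalized Linear Mixed Model (GLMM) featuring logistic regression". Centre is a random effect and the level is two-sided 5%.
- Section 14.1: "All the efficacy analyses will be conducted on the FAS population". That set is everyone randomised, so patients with no month-15 score also need a status.
- Section 14.5: "Missing values will be imputed using a linear model estimated on the Placebo group". Covariates, rounding and residual draws are not mentioned. For an early visit outside the (unstated) time frame, "the data of the early interruption visit will not be included in any of the inferential analyses".
- The amendment table at the front of the document: "Due to incomplete data in the dose 2 arm, the missing data will be evaluated as described in the section 14.5 of the protocol".

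Appendix 2 makes ONLS the sum of two whole-number grades (0 to 12). Section 14.5 also promises an evaluation of the impact of missing data and sensitivity analyses by other approaches, with detail left to the SAP. Section 14.1 repeats efficacy analyses on the per-protocol set.

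**The concern.** For observed scores the definition works: improving means a fall of at least one point. A linear prediction is fractional and is pulled towards the Placebo mean, so it has far less spread than a real score. A cut-off applied to it does not return the true proportion of improvers.

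If both arms had the same small amount of imputation, the error would largely cancel. Dose 2 was stopped on 18 September 2017 while Placebo continued, so many more dose 2 patients are imputed at month 15. An unstated coding choice could then produce, or hide, a dose 2 responder result.

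**Working it through.** **1. Inputs.** From Section 14.3: SD 1, correlation 0.75, compound symmetry, 100 per arm, 10% drop-out. These reproduce the plan's sample size. The variance of the two-visit mean adjusted for baseline is (1 + 0.75)/2 − 0.75² = 0.3125, so n = 2 × (2.241 + 1.282)² × 0.3125/0.3² ≈ 87 per group (88 with the t correction), against 89 stated. The plan gives no figure for the responder analysis. Assumed: baseline mean 3, even recruitment over the planned year, missingness unrelated to outcome.

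**2. How much of dose 2 is imputed.** 18 September 2017 minus 450 days is 25 June 2016. A 366-day recruitment year ending between 1 October and 31 December 2016 leaves 98/366 = 27% to 189/366 = 52% short of Day 450. If early visits within 45 days are shifted to month 15, this becomes 53/366 = 15% to 144/366 = 39%. The range is therefore about 15-52%.

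**3. Why the cut-off fails.** With slope 0.75, baseline b and Placebo drift d, the predicted change is d − 0.25(b − 3). Scores are treated as a rounded normal with mean 3 and SD 1. At d = 0:
- b = 4 gives 3.75: a fall if any decrease counts, no change if rounded.
- b = 3 gives no change, so estimation error tips it either way.
- b = 5 gives 4.5, on the rounding edge.

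Any-fall responders are therefore 1 − Φ(0.5) = 31%, plus about half of the 38% at b = 3, or about 50%. Rounded responders are about 1 − Φ(1.5) = 7%. A required full predicted point gives about 0%. The true rate in this set-up is 25.7%.

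**4. Effect on the comparison.** Difference = (dose 2 fraction missing − Placebo fraction missing) × (imputed rate − true rate). With 40% and 10% missing:
- Any fall: 0.30 × (0.50 − 0.257) = +7.3 points (simulated +7.3).
- Rounded: 0.30 × (0.067 − 0.257) = −5.7 points (simulated −5.9).
- Full point: 0.30 × (0 − 0.257) = −7.7 points (simulated −7.6).

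**5. False findings.** Simulation with no drug effect, zero drift, baseline mean 3 and 10% drop-out in addition to the stop; nominal 2.5% per side. Ranges cover two ways of generating scores and two tests (logistic GLMM and two-proportion z-test). Later scores means month 6, or months 6 and 12.

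| Dose 2 stopped | 15% | 27% | 39% | 52% |
|---|---|---|---|---|
| Any fall, baseline-only model: for dose 2 | 6% | 15-18% | 28-35% | 45-53% |
| Any fall, later scores added: for dose 2 | 6-7% | 14-17% | 26-31% | 44-52% |
| Rounded, baseline-only model: against dose 2 | 6% | 11% | 19-23% | 40% |
| Rounded, later scores added: against dose 2 | 3-4% | 4-5% | 7-8% | 10-12% |

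**6. Sensitivity to drift.** Any fall, baseline-only model, 39% stopped: 28-35% at zero drift, 12-13% at 0.1 points of Placebo worsening, 8% at 0.2, 4% at 0.3 and 1-2% at 0.4. Step 3 shows why. At d = 0.4 a baseline of 4 is predicted to worsen by 0.15, so only b ≥ 5 (7%) counts, below a true rate of 12%. In 72 settings (baseline mean 2.6-3.5, drift −0.2 to +0.4, three covariate sets) the rounded rate was below the true rate every time. The any-fall rate was above it in 68; the 4 exceptions all had a baseline-only model and worsening of at least 0.2.

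**7. Sensitivity to baseline mean.** Any fall at 39% stopped and zero drift ranges over about 27-42% for means 3.25 and 2.75.

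**8. Keeping the residual.** Adding a residual draw and then rounding gives about 27% responders among the imputed against 25.7% true, and under 4% false findings in total at 39% stopped.

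**The case against.** The strongest reply is that the detail may exist elsewhere. Section 14.5 defers to a SAP whose further text is not in the supplied document, and one reading (residual draw, then rounding) is nearly unbiased. That stands: the claim covers only what is supplied, and a full SAP may settle it.

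A reader might infer that the two simple readings always err in opposite directions. The documents do not support that. Section 6.4 describes near-stability of ONLS over a year on placebo, which favours low drift. But Section 14.5 opens its case against carrying values forward with "Due to likely expected loss of efficacy after treatment discontinuation" and allows for deterioration, and Section 8.4.1.3 reports ONLS worsening over five years. With enough worsening both readings lean against dose 2.

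The table's later-scores rows are approximate, because month-12 availability for stopped patients depends on the unstated visit-shift window.

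The per-protocol repeat and promised sensitivity analyses are real mitigation, but they do not correct the main responder analysis.

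A reader might also see a conflict between end of treatment (Section 8.4.1.2) and 15 months (Section 14.4). Section 10.5 says: "Treatment should be taken until the last visit (at 15 months", so the labels coincide for completers, and Section 14.5 bars an out-of-window early visit under either. Nor does the absence of a stated baseline term in the responder model inflate type I error (4.6% without, 4.4% with).

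**Conclusion.** The concern holds in this form: if responder status is taken from the Placebo-model predicted mean, the dose 2 comparison is biased with no drug effect. Rounding, or requiring a full predicted point, understates dose 2 responders in every setting checked. Counting any fall overstates them when Placebo is nearly stable, and this fades or reverses as Placebo worsens. The mechanism follows from the plan's own SD and correlation. The percentages rest on the assumed baseline mean, drift, recruitment pattern, missing fraction and outcome-independent missingness.

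The reach is one secondary endpoint. Nothing here touches the primary ANCOVA on mean ONLS, which needs no yes/no coding. The rule should be settled before unblinding.

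**What to change.** 1. State that responder status is not derived from a predicted mean. Use multiple imputation with whole-number ONLS draws that keep residual variation, from the Placebo-based model of Section 14.5, with baseline and every observed month 6 and month 12 ONLS score as covariates. In each completed data set, define a responder as a fall of at least 1 point at 15 months, then combine by Rubin's rules.
2. Among the sensitivity analyses already promised, name observed cases only, and within-arm imputation for product-stop missingness (which assumes the stop is unrelated to outcome).
3. Add baseline ONLS as a fixed effect in the responder GLMM, as in the primary model. Power with complete data rises from about 69-71% to 73-74%. This is a small gain, not an error correction.

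**Cost.** SAP wording and a little programming; all scores are already collected. Placebo-based draws are conservative (about 0.1-2.6% null rejections at a nominal 5%) and dilute a real dose 2 effect. For a 0.3-point effect present from month 6, power across 15-52% stopped is about 60% down to 30% with months 6 and 12 in the model, and 43% down to 8% from baseline only; it helps less if the effect appears late. Within-arm draws (55-63% power, 3-5% null rejections) and observed cases (50-67%, 3-7%) are better calibrated when the stop is unrelated to outcome, so they should be shown beside the main result. Keeping the Placebo basis as the default follows Section 14.5; it is a choice, not a statistical necessity.
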